five times higher than the rate after THA for osteoarthritis. Dislocation involves separation of the prosthetic femoral head and acetabular cup and requires closed reduction of the prosthesis under sedation or general anaesthetic to restore a patient's ability to ambulate. For irreducible or recurrent cases, a revision THA may be required. Treatment of recurrent instability is associated with significant costs and decreased patient quality of life.^{14,15} Closed reduction and revision THA incur additional hospital costs of 19% and 148% of an otherwise uncomplicated THA, respectively.¹⁵ Currently, patients undergoing a THR are routinely informed about the risk of dislocation prior to their surgery. Medical and allied health staff often provide "hip precautions" which require patients to restrict their post-operative activity to minimise the risk of dislocation.¹⁶ These restrictions (not flexing beyond 90 degrees, not sitting in deep chairs, not crossing legs) are disruptive to usual activity and are a source of anxiety during recovery as patients are constantly reminded of the risk of dislocation.¹⁷

Dual mobility cup (DMC) has been proposed as an alternative, novel design for THA that is purported to reduce the risk of dislocation in high-risk populations such as femoral neck fractures. The DMC theoretically increases stability by providing an additional articulating surface ('ball-within-ball') compared to traditional THA designs (Figures 1-3).¹⁸ This is achieved by use of a larger head-to-neck ratio and jump distance (i.e. vertical or inferior head displacement required for dislocation) that approximates the size of the natural femoral head (and the size of a hemiarthroplasty) allowing an increased range of motion in all directions before dislocation occurs. In standard THA, impingement of the neck against the polyethylene liner at a single articulation creates a lever effect, increasing the risk of dislocation. In the setting of elective THA performed for osteoarthritis, use of DMC is associated with a significantly decreased risk of dislocation compared to conventional THA in the first post-operative year for both primary and revision THR procedures.¹⁹

[figure not shown]

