Cost-benefit analyses have demonstrated significant savings associated with a reduced incidence of dislocation for primary THA performed for osteoarthritis. Economic modelling of a French cohort assuming a relative risk of dislocation of 0.4 for DMC compared to conventional THA reported 3,283 less dislocations and 882 less revision surgeries at a cost saving of €28.3 million per 100,000 THA procedures.²⁶ Similarly, analysis of direct and indirect costs using administrative and registry databases from the United States demonstrated net cost savings per dislocation saved at a cost difference threshold of \$1,023 (2013 USD) more for DMC implants.²⁷ The DMC design of THA therefore has the potential to reduce the cost burden associated with closed reductions and revision THA performed for instability in a high risk population. A recent editorial from a leading orthopaedic journal called for a high quality, adequately powered trial to determine if routine use of DMC can address the problem of the high rate of dislocation associated with the use of THA in people with fractured neck of femur.²⁸

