1.6 Secondary Aim

- To compare the revision rates (for dislocation and for any reason) at one, two and five years post-operatively.
- To determine the cost-effectiveness of using DMC compared to conventional THA in reducing the risk of hip dislocation in a hip fracture population.
- To compare the mortality between groups at 30 days, 120 days, and then at one, two and five years post-operatively.

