2.14 Statistical analysis

The analysis for the primary aim will test between-group difference in the proportion of cases sustaining a dislocation of the affected hip within one year post-operatively. The primary analysis will use cluster summary methods. These methods estimate the treatment effect using cluster level differences and have been shown to be appropriate for cluster randomised crossover trials with rare outcomes and the intracluster and interperiod correlation coefficients expected in this trial. Multiple imputation will be used to account for missing outcome data, using auxiliary variables gathered from routine AOANJRR data (including age, sex, baseline health, pain and function, diagnosis and surgical factors).

Secondary analyses will be performed for the primary outcome, to test for differences in treatment effect between subgroups of patients: surgical approach, ASA grade, BMI grade and gender. The analysis method will be the same as the primary outcome and will include an interaction term between subgroup and treatment group.

Secondary analyses will include an analysis of all-cause revision, revision for dislocation, and other complications (death, re-operation and readmission rates). Cluster summary methods will be used for all secondary analyses.

If DMC are found to be superior to conventional THA, a cost effectiveness analysis of DMC compared to conventional THA will be performed from a health system perspective, calculating the cost per dislocation saved. The only difference in input costs will be the difference in implant costs, as all other care costs will be equal.

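### The cost-effectiveness rule treats implant price as the only cost difference, so it leaves out the treatment cost of the dislocations that DMC would avoid

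*Protocol*

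**What the plan says.** Section 1.6 lists this secondary aim: "To determine the cost-effectiveness of using DMC compared to conventional THA in reducing the risk of hip dislocation in a hip fracture population". Section 2.14 sets the condition, "If DMC are found to be superior to conventional THA, a cost effectiveness analysis", and the form of the result: it "will be performed from a health system perspective, calculating the cost per dislocation saved". The costing rule follows directly: "The only difference in input costs will be the difference in implant costs, as all other care costs will be equal".

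Section 1.2 says what a dislocation costs: "Closed reduction and revision THA incur additional hospital costs of 19% and 148% of an otherwise uncomplicated THA, respectively". It then says that DMC has the "potential to reduce the cost burden associated with closed reductions and revision THA performed for instability in a high risk population". In support it cites a French model of primary THA for osteoarthritis that "reported 3,283 less dislocations and 882 less revision surgeries at a cost saving of €28.3 million per 100,000 THA procedures", and a US analysis that found net savings at an implant cost difference of $1,023.

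Item 1.8.5 of section 1.8 repeats the superiority condition and points to a list further down. The only list that follows is the classification of complications.

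**The concern.** The analysis runs only once the trial has shown fewer dislocations with DMC. At that point the two arms differ in the number of events that the protocol itself prices. Taking all non-implant care costs as equal therefore conflicts with the condition that triggers the analysis, and with the economic argument in section 1.2.

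At stake is the answer to a declared secondary aim. If implant price is the only cost that may differ, any positive price difference gives a positive cost per dislocation saved. A dearer implant could then never be shown to be cost saving, although both economic analyses cited in section 1.2 report savings from fewer dislocations.

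**Working it through.** **Inputs**

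- Planned rates of 6% and 3%, so the risk difference RD = 0.03 (section 2.3).
- Closed reduction 0.19 C and revision 1.48 C, where C is the cost of an uncomplicated THA (section 1.2).
- Share of dislocations revised, r. No value is given for this population. The documents allow two rough figures:
  - Section 2.3: 3.0% revised at one year × 32.5% of revisions for dislocation = 0.975%. Divided by the 6% target, r ≈ 0.16. This assumes that the 32.5% share, which is not specific to one year, applies at one year.
  - Section 1.2, French model: 882 / 3,283 = 0.269. This is an osteoarthritis model and serves only as illustration.
- Implant price difference, dC: not given, so values below are assumptions.

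**The plan's own figure.** The protocol states no cost-effectiveness result. Its sample size, from which RD is taken, does reproduce. For 6% against 3% at 80% power and two-sided 5%, 749 per group are needed. The design effect is 1 + 15(0.01) − 16(0.008) = 1.022. Then 749 × 1.022 × 2 = 1,531, against 1,536 stated.

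**Formulas**

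- Ratio under the stated rule: dC / RD.
- Ratio with avoided treatment costs: dC / RD − c, where c is the treatment cost of one dislocation, other complication costs being equal.
- c = 0.19(1 − r) + 1.48r if revised cases have no separate closed reduction, or c = 0.19 + 1.48r if they have both.

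**Cost omitted per dislocation avoided, and per patient (c × 0.03)**

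| r | c, revision replaces reduction | c, both incurred | Per patient |
|---|---|---|---|
| 0 | 0.19 C | 0.19 C | 0.57% of C |
| 0.16 | 0.40 C | 0.43 C | 1.2% to 1.3% of C |
| 0.269 | 0.54 C | 0.59 C | 1.6% to 1.8% of C |

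**Effect on the ratio, for assumed price differences**

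| dC (assumed) | Stated rule | c = 0.19 C | c = 0.40 C | c = 0.59 C |
|---|---|---|---|---|
| 5% of C | 0.05/0.03 = 1.67 C | 1.48 C (13% too high) | 1.27 C (32%) | 1.08 C (54%) |
| 10% of C | 0.10/0.03 = 3.33 C | 3.14 C (6%) | 2.93 C (14%) | 2.75 C (21%) |

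**Break-even.** With avoided costs included, DMC is cost saving when dC is below RD × c: 0.57% of C for closed reduction only, and 1.76% of C at c = 0.59 C. Below those thresholds the stated rule still reports a positive cost.

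**The case against.** The best defence is that input costs means the cost of delivering each treatment. That fits the design: each surgeon keeps the same stem, fixation and approach (section 1.3), surgery and rehabilitation are standardised (section 2.9), and no extra treatment is given (section 2.10). On this reading the sentence says only that index-episode costs differ by the implant, which is reasonable, and the list mentioned in item 1.8.5 might supply the downstream items. The reading is possible, but the clause on all other care costs tells against it. The list is headed as complications rather than costs, and nowhere does the protocol say that downstream costs will be netted off. Even if index costs were meant, the sentence needs restating.

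A second defence is that an implant-only ratio is still interpretable, because a reader can set it against the cost of treating one dislocation, and no decision rule is attached to it. That is true, but such a ratio is not the health-system figure that section 2.14 promises.

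Third, the direction of the error is not certain. DMC could raise other readmission or reoperation costs, which the trial has yet to measure. This stands as a condition on the conclusion.

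A reader might also infer from section 1.6 that the analysis must be run whatever the primary result. The documents do not support that. Section 1.6 states an aim without saying when the analysis is run, and sections 1.8 and 2.14 agree on the superiority condition. Making the analysis conditional is a design choice, and a cost per dislocation saved is unstable or undefined when none are saved.

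**Conclusion.** The point holds as an error in a stated rule. Followed literally, section 2.14 omits 0.19 C per dislocation avoided if closed reduction is all that is needed, and roughly 0.40 C to 0.59 C if about 16% to 27% of dislocations are revised. At the planned 3-point reduction this is about 0.6% to 1.8% of C per patient. The ratio is too high by that amount per dislocation, provided DMC does not add offsetting complication costs. The percentage error depends on the implant price difference and cannot be stated from the protocol.

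A reader might take 1.48 C as the possible size of the error. That would require every dislocation to be revised, whereas section 1.2 reserves revision for irreducible or recurrent cases. Nor do the documents give any basis for a revised share as high as one third.

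The consequence is limited to a secondary analysis that may not be run. The primary outcome, sample size and data collection are unaffected. It should be corrected before analysis, but it is not critical to the trial.

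**What to change.** Replace the costing sentence in section 2.14 with wording such as: *Index-episode costs are assumed equal between the arms apart from the implant. Incremental cost is the difference in implant cost plus the between-arm difference in the cost of linked closed reductions, readmissions, reoperations and revisions within one year. The cost per dislocation saved will be reported with its uncertainty.* Make item 1.8.5 point to the cost items actually used.

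This definition favours neither arm, since extra complication costs under DMC would enter in the same way as savings. The superiority condition can stay.

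The change costs a wording amendment, a table of unit costs and a little more analysis. Sections 2.11 and 2.13 already provide for dislocation, complications, readmission and reoperation through linkage and for revision through the registry, so no new outcome data are needed.

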2.15 Operative Record

As above no standard processes will change regarding the operative record collected by the AOANJRR.

2.16 Data Access

All principal investigators involved in data analysis will have access to deidentified datasets. All principal investigators involved in subcommittees will have access to relevant deidentified data necessary for undertaking their specific role (e.g. outcome validation).

3. Study Approvals and Dissemination

3.1 Ethics & Site Approvals

All ethics and site approvals will be obtained prior to commencing patient recruitment at participating sites. Ethics approval will be obtained through an institutional Human Research Ethics Committee (HREC) or through a central HREC if the site accepts approvals through National Mutual Acceptance. Following approval, the study will be submitted to local ethics committees and Research Governance Offices as required for each site.

3.2 Amendments

Any modifications to the protocol which may impact on the conduct of the study, potential benefit of the patient or may affect patient safety, including changes of study objectives, study design, patient population, sample sizes, study procedures, or significant administrative aspects will require a formal amendment to the protocol. Such amendment will be agreed upon by the Steering Committee and approved by the Ethics Committee prior to implementation and site notification.

Administrative changes of the protocol are minor corrections and/or clarifications that have no effect on the way the study is to be conducted. These administrative changes will be agreed upon by Trial Management Committee and will be documented in a memorandum. The Ethics Committee may be notified of administrative changes at the discretion of Trial Management Committee.

3.3 Consent

Individual consent is not being sought for randomisation. This is because randomisation is not occurring at the patient level and because both treatments represent current standard practice. Patients are not usually consented or informed regarding the specific type of THA used in hip fracture surgery (e.g. type of articulation, bearing surface, implant fixation method or use of DMC). The DISTINCT study will use the same waiver of consent process as the CRISTAL study which has received ethics approval (Reference: X18-0424 & HREC/18/RPAH/603). Participants will be consented for surgery as per usual practice.

3.4 Governance (Coordinating Centre)

The day to day management of the trial will be the responsibility of the Australian Orthopaedic Association National Joint Replacement Registry (AOANJRR) and South Australian Health and Medical Research Institute (SAHMRI).

Other expert subgroups may be established throughout the project to advise on specific elements and make recommendations should the need arise. SAHMRI is already contracted by the AOA to provide data entry, data management, IT and statistical analysis services to the AOANJRR.

3.5 Risks to Patients

As patients will be treated with the standard protocol for both conventional THA and DMC, this study poses no foreseeable risk, harm or discomfort to patients.

3.6 Data Confidentiality, Privacy and Security

SAHMRI will provide IT, data management and statistical analysis services for this registry-nested study. SAHMRI is contracted by the AOA to provide similar services for the AOANJRR. This collaboration has been very successful at maintaining a high level of data security and data quality for the AOANJRR.

3.6.1 South Australian Health and Medical Research Institute

SAHMRI is South Australia's first independent flagship health and medical research institute. The SAHMRI team working on the AOANJRR consists of a project manager, data managers, statisticians, IT resources and data entry staff. The SAHMRI team contribute crucial data management and analysis expertise to the AOANJRR which will be transferred to the DISTINCT study. This collaboration has been very successful at maintaining a high level of data security and data quality for the AOANJRR. See SAHMRI ICT Security Summary.

3.6.2 Protection and confidentiality

The AOANJRR is required to have highly secure data protection systems to secure the identified information which it currently holds as this is an absolute requirement under its Federal Quality Assurance Activity.

SAHMRI has existing security systems, policies and procedures in place as well as software barriers to protect personal information and ensure confidentiality (Appendix A).

3.6.3 Restrictions to use of data

The data collected as part of standard Registry data collection will continue to be used for Registry activities, any additional data collected specifically for this study will only be used by the AOANJRR for the purposes of this study.

Any data published in reports, papers and publications will be de-identified. Access to identifiable information is limited to authorised AOANJRR and SAHMRI staff.

3.6.4 Patient confidentiality

All patient data will be managed in accordance with the Guidelines for the Protection of Privacy in the Conduct of Medical Research. Patient contact details will only be used for the purpose for which they were collected and will be stored securely and confidentially. Patients will not be identified in any reports, manuscripts or presentations derived from the DISTINCT project.

<https://www.oaic.gov.au/privacy/the-privacy-act/rules-and-guidelines/medical-research/>

3.6.5 Surgeon and Hospital confidentiality

No individual surgeons or hospitals will be identified in any reports manuscripts.

3.7 Data Storage and Record Retention

The SAHMRI Data Management Staff have established security systems which limit access to SAHMRI Data Management and Registry staff only.

There are policies and procedures in place as well as software barriers to protect personal information. These include the use of codes, passwords and encryption.

The proforma used for data collection are stored in a secure locked room at SAHMRI. After a period of two years the forms stored will be optically scanned and electronically stored in the secure SAHMRI database. All data will be retained in accordance with good scientific practice. All electronic data collected will be held for a minimum of 15 years after publication of any final reports and manuscripts. Data quality will be checked monthly under the supervision of the Data Quality Committee.

3.8 Reporting and Dissemination

3.8.1 Reporting

Although identifying information is stored no patient is identified in any Registry reports or publications. AOANJRR Registry reports will only contain deidentified data. This includes any ad hoc reports prepared by the Registry.

There is a requirement to meet standard AOANJRR publication policy requirements which includes having clinical oversight from the AOANJRR and the Statistician involved in the analyses included as authors on the paper). A writing committee will be established to write the principal papers (primary and secondary outcomes).

3.8.2 Dissemination

Dissemination will be by peer reviewed journal publication, conference presentation and through media. All study findings will be reported, regardless of statistical significance or the size or direction of effect.

Study findings will be released to participating sites and investigators.

Input will be sought into guideline development by state and national bodies (e.g. ACSQHC).

The results of the study are expected to be published in a journal with high impact and to be of interest to a wide audience (beyond orthopaedics and geriatricians, including hospitalists and public health).

They are expected to have clinical importance and statistical power that will enable the results to influence practice, which currently lacks studies on this size and quality.

3.8.3 Authorship

Authorship for principal papers will be by the members of the writing committee and the DISTINCT Study Group (consisting of all investigators according to the authorship guidelines of the ICMJE).

3.9 Implementation

Following the study, practice change at departmental and surgeon level will be measured for each surgeon and each site using routine AOANJRR data. Implementation of practice change based on study results is expected to be facilitated by widespread surgeon involvement in the trial and the uncertainty around the superiority of either method.

3.10 Statement for Compliance with NHMRC National Statement on Ethical Conduct of Research Involving Humans

This study will be conducted in accordance with the ethical principles that have their origin from the Declaration of Helsinki and are consistent with ICH/GCP. This study will comply with the National Health and Medical Research Council (NHMRC) National Statement on Ethical Conduct in Research Involving Humans.

<https://www.nhmrc.gov.au/guidelines-publications/e72>

4. Administrative Information

4.1 Registration

DISTINCT will be registered with the Australian and New Zealand Clinical Trials Registry (anzctr.org.au).

4.2 Funding

This study is funded by an Australian Orthopaedic Association Research Foundation (AOARF) grant awarded in October 2019. The funding source had no role in the design of this study and will not have any role in execution, analyses, interpretation of the data, dissemination or decision to publish. The study is also funded by the Whitlam Orthopaedic Research Centre.

4.3 Sponsor

Whitlam Orthopaedic Research Centre, [name].

4.4 Declaration of interests

[name] (IH), [name] (SG), [name] (RdS) and [name] are employed by the AOANJRR.

4.7 Abbreviations

| | |
|---------|--|
| AOANJRR | Australian Orthopaedic Association National Joint Replacement Registry |
| AAOS | American Academy of Orthopaedic Surgeons |
| ANZHR | Australian and New Zealand Hip Fracture Registry |
| DMC | Dual Mobility Cup |
| FNF | Femoral Neck Fracture |
| ICJME | International Committee of Medical Journal Editors |
| NICE | National Institute of Health and Care Excellence |
| THA | Total Hip Arthroplasty |

Appendix A - SAHMRI ICT Security Summary

Confidentiality

- SAHMRI staff have confidentiality clauses in their employment contracts that prohibit the disclosure of confidential information – even after the termination of the agreement in question
- Access to SAHMRI information is revoked on termination of employment
- SAHMRI staff are directed to have a “clean desk” policy to ensure that confidential information is properly secured. These measures mitigate the risk of confidential data being disclosed to unauthorised people, as well as ensuring that conversations about confidential data can take place in a secure location.

Software Patching

- SAHMRI endpoints and infrastructure undergo regular patching activities, as recommended by the applicable vendor (e.g. Microsoft).

Network Security

- SAHMRI employs an endpoint security solution that is deployed to all endpoints providing on-access scanning, application monitoring, as well as regular scheduled scans
- The endpoint security system alerts the SAHMRI ICT team when suspicious activity within the SAHMRI network occurs, and can automatically take appropriate action to mitigate adverse consequences
- Access to the ICT infrastructure is granted to a select group of ICT personnel for the necessary administration of the environment
- Documents and data relating to the AOANJRR project are stored on network file shares to which access is granted to authorized personnel on a least privilege basis
- Access controls are enforced using groups in Active Directory
- Group membership is approved by data owners
- General SAHMRI staff do not have administrator access to desktop machines
- SAHMRI's network is protected by security appliances that actively monitor the environment for suspicious activities
- SAHMRI's email server provides spam filtering and malware protection

Physical Security

- SAHMRI staff, as well as IT administration staff are located at SAHMRI's North Terrace facility in secure areas with multiple levels of swipe card access and no publicly visible windows
- Data is housed in SAHMRI's main server room in its North Terrace site which is physically accessible to a select group of authorised personnel only via card swipe access
- Tape backups of the data are stored securely offsite <https://www.timg.com/service/backup-media-storage>

